Measurement of Heart Rate Variability in critically ill patients: Refinement of data acquisition and analysis

IRAS ID 254530

UK Legal representative

Name of Organisation: University of Liverpool
Name of Representative: [name]
Address: Research Support Office
University of Liverpool / Liverpool Joint Research Office
[name]
[name]
[name]
United Kingdom
[contact]
Email: [contact]

UK NHS R&D Department

Name of Organisation: Royal Liverpool and Broadgreen Univeristy Hospitals Trust
Name of Representative: [name]
Address: [name],
[name]
[contact]
Email: [contact]

Chief Investigator

Name: [name], med. [name]
Address: University of Liverpool
Institute of Ageing and Chronic Disease
[name]
[name]
[contact]
Email: [contact]

Name and address of Co-Investigators

Name: [name]
Address: University of Liverpool
Institute of Ageing and Chronic Disease
[name]
[name]
[contact]
Email: [contact]

Name: [name]
Address: Isansys Lifecare Ltd
[name],
[name]
Phone: Office [name] | Mobile/Cell [name]
Email: [contact]

Name: [name]
Address: Royal Liverpool and Broadgreen University Hospital
Clinical Physics and Medical Engineering Department
[name]
[name]
Email: [contact]

Name : [name]
Address: Royal Liverpool and Broadgreen University Hospital
Clinical Physics and Medical Engineering Department
[name]
[name]
Email: [contact]

Name : [name]
Address: Royal Liverpool and Broadgreen University Hospital
Clinical Physics and Medical Engineering Department
[name]
[name]
Email: [contact]

Name [name]
Address: Institute of Ageing and Chronic Disease
University of Liverpool
[name]
[name]
[name]
Email: [contact]

Study Synopsis and Summary

Title	Measurement of Heart Rate Variability in critically ill patients: Refinement of data acquisition and analysis
Protocol short title / Acronym	
Protocol Version number and Date	Version 1.9 (2 nd February 2019)
IRAS	254530
Study Phase if not mentioned in title	Prospective observational feasibility study
Is the study a Pilot?	Yes – this is Pilot feasibility study
Study Duration	12 months
Methodology	Prospective observational feasibility study
Sponsor	University of Liverpool
UK legal representative	University of Liverpool
Chief Investigator	[name]. med. [name]
REC number	
Medical condition under investigation	Critical illness
Purpose of clinical trial	To investigate if two devices to monitor and capture Heart Rate Variability (HRV) and ECG data in Critically ill patients produce comparable results.
Primary objective	To describe the robustness of data on HRV obtained by two different monitoring systems during daily care of critically ill patients.
Secondary objective	
 1. To identify the most suitable and cost-efficient device for HRV monitoring in critically ill patients. 2. To define amendments in data capture and analysis required to proceed to a larger clinical trial
Number of Subjects	30 patients

Trial Design	Prospective observational feasibility study
Endpoints	
Primary outcome:
 
 • Number of interpretable HRV epoch episodes for each device and comparison between Isansys device and gold-standard holter monitoring (Isansys and Holter Monitor) 
Secondary outcomes:
 
 • Correlation of HRV time domain, frequency domain and non-linear HRV measures analysis between Isansys wireless monitoring patch and Holter monitoring • Correlation between HRV and onset of arrhythmias • Correlation between HRV and cardiorespiratory events (desaturation, drop in blood pressure >20%, change in ventilator settings) • Nurses' and medical staff's perception of the usability of both monitoring systems in daily routine practice
Main inclusion and Exclusion Criteria	
Inclusion criteria:
 
 • Adult patients ≥18 years • Expected stay in the ICU >48 hours • Sinus rhythm on ITU admission • Mechanically ventilated patients 
Exclusion criteria:
 
 • Non-ICU patient • History of Atrial Fibrillation • Inability to obtain consent
Randomization	Not applicable
Study procedure	
If all inclusion criteria are met and no exclusion criteria are present, patients will be eligible, invited to participate and informed consent will be sought.
 
Continuous ECG data will be recorded using two different devices. ECG data will then be processed to derive HRV using the methodology

Descriptive statistics showing means \pm standard deviation (SD) for continuously distributed variables, and number and proportions for categorical variables will be used for all comparisons. Chi-square tests will be used for categorical outcomes unless assumptions of the test are found to have been violated, in which case Fisher's exact test will be used.

Parametric and nonparametric methods, as determined by the distribution of each variable, will be used to test statistical significance of continuous variables. Logistic regression will be utilized to assess the predictive value of HRV different outcomes (onset of arrhythmias, change in ventilatory setting, drop in blood pressure, desaturation) adjusting for covariates. Bland-altmann methodology will be used to assess the comparability of results between each HRV monitoring device (Isansys and Holter monitor).

Abbreviations used in study protocol

AF	Atrial Fibrillation
CRF	case report form
CRP	C-reactive protein
ECMO	extracorporeal membrane oxygenation
GCP	Good Clinical Practice
GP	General Practitioner
HRV	Heart Rate Variability
HF	High Frequency Domain
IQR	Interquartile Range
ICU	intensive care unit
LOS	Length of stay
LV	Left ventricle
LA	Left atrium
LF	Low frequency domain
LF/HR	Low frequency/High Frequency ratio
NN	Normal-Normal Interval
pNN50	Percentage of RR intervals that differ by greater than 50ms
RCT	randomized controlled trial
REC	Research Ethics Committee
RR	R-R Interval
RMSSD	Root mean square of successive RR intervals
SAPS	Simplified Acute Physiology Score
S	Area of ellipse of Poincare plot which represents total HRV
SD	standard deviation
SD1	Poincare plot standard deviation perpendicular to the line of identity
SD2	Poincare plot standard deviation along the line of identity
SD1/SD2	Ratio of SD1 to SD2
SDNN	Standard Deviation of NN interval
SDANN	Standard deviation of the average NN interval
VLF	Very low frequency domain
ULF	Ultra low frequency domain

Glossary of Research Terms and Abbreviations

AE	Adverse Event
AR	Adverse Reaction
ASR	Annual Safety Report
CA	Competent Authority
CI	Chief Investigator
CRF	Case Report Form
CRO	Contract Research Organisation
DMC	Data Monitoring Committee
ICF	Informed Consent Form
Main REC	Main Research Ethics Committee
NHS R&D	National Health Service Research & Development
PI	Principle Investigator
QA	Quality Assurance
Participant	An individual who takes part in a clinical trial
RCT	Randomised Controlled Trial
REC	Research Ethics Committee
SAE	Serious Adverse Event
SDV	Source Document Verification
SOP	Standard Operating Procedure
TSC	Trial Steering Committee

1. Introduction

The healthy cardiovascular system is in a state of dynamic stability.¹ This stability is achieved by altering heart rate, blood pressure and other factors to react to internal and external stressors.¹ Alterations in heart rate and blood pressure is under the control of the autonomic nervous system. HRV analysis is a method used to assess cardiac autonomic function.² Heart rate variability analysis assesses the variability between heart beats which reflect alterations in heart rate due to fluctuations in the autonomic nervous system.³ HRV is therefore considered a measure of neurocardiac function that reflects heart-brain interactions.⁴

Autonomic dysfunction is often seen in critically ill patients' and as part of disorders requiring admission to the intensive care unit.⁵ Assessment of the autonomic nervous system may provide information regarding pathophysiology, severity and prognosis associated with these disorders.⁵ Depressed HRV has been associated with increased 30-day all-cause mortality in intensive care unit patients.⁶ Furthermore alterations in heart rate variability have been recognised in sepsis, multiorgan dysfunction syndrome, acute ischaemic stroke, traumatic brain injury, Guillain-Barre syndrome and following myocardial infarctions and malignant arrhythmias.⁵

HRV analysis has seen a significant increase in clinical use since the 1960's. However the significance and meaning of many different HRV measures has led to the potential for incorrect conclusions and interpretations.² In 1996 the European Society of Cardiology and the North American Society of Pacing and Electrophysiology published guidelines for the Standard of measurement, physiological interpretation, and clinical use of heart rate variability.² The goal of these guidelines was to, 'standardise nomenclature and develop definitions of terms; specify standard methods of measurement; define physiological and pathophysiological correlates; describe currently appropriate clinical applications and identify areas for future research.'² These guidelines continue to form the basis and define the conduct of much of the research into HRV.

The European society of cardiology guidelines recognised a number of different HRV measures. Time domain measures are the simplest method of analysis of HRV. In a continuous ECG recording, the time between adjacent R wave peaks of QRS complexes is detected. This time interval is termed the N-N interval. Simple statistical tests are then applied to the N-N interval to determine the HRV, these include the standard deviation of the N-N interval (SDNN), square root of the mean squared differences of the N-N interval (RMSSD), the number of interval differences of successive N-N intervals greater than 50ms (NN50), and the proportion derived by dividing NN50 by the total number of NN intervals (pNN50).² Frequency domain measures

make use of power spectral density analysis and fast fourier transform analysis to provide information on how power distributes as a function of frequency.² This technique splits the ECG waveform into small subunits/epochs of time depending upon whether high frequency, low frequency or very low frequency measures are required (see below). The epochs of ECG waveform recording is then transformed from a temporal signal into a spectral representation whereby ECG signal is expressed as the sum of multiple sinusoidal waves of a given amplitude and frequency. These amplitudes are then plotted to give the power spectrum by plotting power versus frequency. Spectral components include frequencies measured HF domain(0.15-0.4Hz) thought to represent the parasympathetic input, LF domain (0.04-0.15Hz) thought to represent the sympathetic nervous system and the parasympathetic nervous system, VLF domain (<0.04Hz) and the ultra-low frequency (ULF) domains (<0.003Hz).²⁷ Measurement of the frequencies can be made in absolute values, but are often recorded as normalised units which represents the relative value of each power component in proportion to the total power minus the VLF component.⁸² Non-linear methods include measures such as the Poincare plot.² In the Poincare plot an individual's N-N interval is plotted against time and standard deviation used to interpret changes.⁹ The Poincare plot is described by two descriptors, SD1 is the fast beat-to-beat variability in the R-R intervals whilst SD2 describes the longer variability.^{9,2} SD1 reflects mainly the parasympathetic component of the autonomic nervous system, whilst SD2 reflects the parasympathetic and sympathetic components.⁹

A recent systematic review of the use of HRV evaluated the methodology and design of HRV studies in critical care.³ Karmali et al revealed that over 230 studies have been published considering HRV in critical care.³ These studies published in the critical care literature differed vastly in trial design, methodology, confounding and data was inconsistently reported.³ Details on the time duration of recordings, epochs used in analysis and patient position was not reported in the majority of studies.³ Furthermore, many of the studies did not detail methods to detect artefact or describe how artefact was managed.³ These are significant failings, as ECG recording in the critically ill frequently suffers interference and physiological artefacts.³ Variability analysis should be free from artefact and suffer minimal noise:signal ratio.¹⁰ Artefact removal for HRV analysis often requires premature atrial beat or ventricular ectopic beat removal and appropriate interpolation of ECG QRS complexes. Alternatively techniques such as Poincare have been developed to allow automatic identification and removal of artefact.¹⁰

Each technique for the measurement of HRV represents a unique and distinct means of characterising a series of data in time.¹⁰ However, a number of factors can affect HRV measures regardless of the technique used. Standing and head up tilt are known to increase sympathetic activity. Similarly deep breathing and sighs have been shown to alter HRV indices as have alterations in blood pressure and the baroreflex.¹⁰ These factors should be taken into account

irrespective of what measurement technique is employed. The duration of measurement for analysis should also be taken into account. Dependent upon analysis technique the duration of measurement can range from 2 minutes to 24 hours. There remains significant debate as to the optimal duration of measurement, but in general terms this should be suitable for the technique and explained fully in studies.^{10,2} Despite the number of studies using HRV in critical care there remains significant heterogeneity in methodology.³ This uncertainty has led to the need to clarify the factors that can impact upon HRV recording and analysis in the critically ill population. Karmali et al highlight the need for consensus guidelines relevant to critical care medicine.³ The present study hopes to address these issues and compare the robustness of HRV measures obtained from two separate devices under consideration for use in further research at the Royal Liverpool University Hospital.

The devices to be used in this study will be:

1. The Isansys Lifetouch cardiac monitor is a wireless CE marked device produced by Isansys Lifecare Limited. The Isansys lifetouch cardiac monitor continuously records filtered ECG sampled at 1000Hz. ECG data is transmitted and stored in a wireless interface called the Patient Gateway and Lifeguard Server.
2. A Holter monitoring device that is CE marked and validated for medical grade continuous ECG recording. Holter monitoring is considered the gold-standard monitoring for ECG signal analysis. The Holter device will consist of a 12 lead ECG that will record continuously for 72 hours. ECG data will be recorded to a memory card and the ECG data analysed using standard software. The signal will be sampled at 1000Hz.

Whilst both monitoring devices are capable of recording continuous ECG and HRV data, it remains unclear how robust the data are with regards to interference and artefacts. In particular, it is unclear how each monitoring device will operate whilst patients are undergoing daily care maneuvers such as physiotherapy, washing and patient repositioning. Furthermore, it has not been described yet how HRV is affected by interventions such as mechanical ventilation, administration of inotropes or vasopressors, paralysis agents, or renal replacement therapy. The current study aims to elucidate the impact of these standard interventions on HRV and the robustness of HRV measurement between the Isansys wireless monitor and the gold-standard HRV monitoring technique. This feasibility study will aide decision making with regard to which device will be most suitable for further studies of HRV in critically unwell patients.

2. Trial Objectives, Design and Statistics

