2.1 Trial objectives

The **primary objective** is:

- To describe the robustness of data on HRV data obtained by two different monitoring systems in daily care of critically ill patients. The Isansys wireless monitoring device will be compared to the gold-standard holter monitoring device for ECG analysis.

The **secondary objectives** are:

- To identify the most suitable and cost-efficient device for HRV monitoring in critically ill patients.
- To define amendments in data capture and analysis required to proceed to a larger clinical trial
- To generate preliminary data on the variation of HRV in a critical care patients.

Primary outcome:

- Number of interpretable monitoring epochs in each HRV monitoring system after elimination of artefacts, extra beats and interference

Secondary outcomes:

- Correlation and comparison of HRV time, frequency and non-linear measures between the Isansys monitoring device and the gold-standard holter monitoring system.
- Correlation between HRV and onset of arrhythmias (ventricular or atrial)
- Correlation between HRV and cardiorespiratory events that commonly occur in critically ill patients, including, oxygen desaturation (SaO₂<85%), variations in blood pressure of >20%, change in ventilatory support, muscle paralysis, position of the patient, administration of vasopressors (e.g. noradrenaline and vasopressin).
- Nurses' and medical staff's perception of the usability of both monitoring systems in daily routine

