Parametric and nonparametric methods, as determined by the distribution of each variable, will be used to test statistical significance of continuous variables. Logistic regression will be utilized to assess the predictive value of HRV for different outcomes (mortality, ventilator free-days, length of stay, SOFA score) adjusting for covariates.

3. Sample Size, Selection and Withdrawal of Subjects

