4.3 Schedule of study procedure

With informed consent, the following routinely recorded clinical and laboratory data will be collected:

- Baseline demographics and comorbidities
- Administration of beta blockers or anti-arrhythmics
- Administration of sedative agents (general anaesthetics/opioids/benzodiazepines)
- Reasons for admission to ICU
- Daily biochemistry and haematology results
- Severity of illness scores, including APACHE II and daily SOFA scores
- Daily CAM ICU scores / delirium
- Daily cardiac rhythm as per nursing entry or clinical diagnosis
- Daily clinical parameters, including medications (vasopressors/ionotropes/steroids/muscle relaxants) and organ support
- Daily AKI stage, including treatment with RRT

After obtaining informed consent, continuous ECG data will be recorded using the two different devices. ECG data will then be processed to derive HRV using the methodology described by the European Society of Cardiology Taskforce guidelines.² Processing of ECG data entails checking

for and removal of extrasystole and ectopic beats with interpolation of QRS complexes as described elsewhere.² Continuous 24 hour ECG recording will then be divided into 5 minute epochs for which short term HRV values will be calculated. HRV will be calculated in the time domain, frequency domain and non-linear domains for each 5 minute epoch. Entire 24 hour ECG recordings will be used for long term HRV measures in the time domain, frequency domain and non-linear domains as described the Taskforce guidelines.² HRV data will then be analysed according to that described in the statistical methodology and analysis section. HRV data will be calculated by the Medical Engineering and Clinical Physics department at the Royal Liverpool and Broadgreen University Hospital. They will be blinded to any patient identifiable or clinical information.

Daily data will be collected until day 5 in ICU, day of discharge from ICU or day of death (depending on what occurs first). In addition, we will record ICU and hospital length of stay, ICU and hospital mortality and occurrence of arrhythmias during ICU stay, after 30 days, and after 90 days following enrollment. Data will be collected by accessing routinely available results in the patients' medical records, and if necessary, by contacting the patient's General Practitioner (GP).

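### The synopsis names logistic regression for bedside events that can recur within a patient and fixes no row unit; read plainly, the model suits neither 5-minute epochs nor one row per patient

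*Protocol*

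**What the plan says.** The Statistical Methodology and Analysis entry of the synopsis fixes the model: "Logistic regression will be utilized to assess the predictive value of HRV different outcomes", namely "onset of arrhythmias, change in ventilatory setting, drop in blood pressure, desaturation) adjusting for covariates". The secondary outcomes in section 2.1 include "Correlation between HRV and cardiorespiratory events that commonly occur in critically ill patients".

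The predictor is defined in section 4.3: "Continuous 24 hour ECG recording will then be divided into 5 minute epochs for which short term HRV values will be calculated". The same section adds a second, coarser version: "Entire 24 hour ECG recordings will be used for long term HRV measures". By sections 1 and 6.2 the Holter records for 72 hours.

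Section 2.3 repeats the logistic regression sentence with another outcome list: "for different outcomes (mortality, ventilator free-days, length of stay, SOFA score) adjusting for covariates". Neither place states whether a row is an epoch, a day or a patient, how HRV is linked in time to an event, or how repeated observations on one patient are handled. Section 3.1 gives the question for AF as how HRV changes before onset. The number of patients is 30 in the synopsis and section 4.5, and 40 in section 3.1.

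**The concern.** Plain logistic regression assumes independent rows. Here many rows come from few patients, and both HRV and event risk probably differ between patients; the protocol's introduction itself links HRV to severity and prognosis. Pooling epochs makes the standard error too small. It also mixes two associations: patients with low HRV overall may have more events, and HRV may move before an event within a patient. Collapsing to one row per patient removes the dependence but discards the timing. Section 3.1 wants these analyses to inform a larger trial, so a spurious HRV signal could be carried into its design.

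**Working it through.** **1. The plan's own figure.** The only number offered for the HRV-event analyses is the AF count in section 3.1: 2-3 cases in 40 patients at an incidence of 13.8%. But 40 × 0.138 = 5.5 (and 30 × 0.138 = 4.1); 2-3 of 40 would need 5.0% to 7.5%. The figure does not reproduce. That is a separate point. Here it shows only that, on either count, AF cases are too few for covariate adjustment at patient level.

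**2. Number of rows.** 24 × 60 / 5 = 288 epochs per day and 3 × 288 = 864 per 72 hours. That is 30 × 864 = 25,920 or 40 × 864 = 34,560 rows.

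**3. Approximate false-positive rate with pooled epochs.** The design effect is D = 1 + (m − 1) × ICC(HRV) × ICC(event). The true size of a nominal 5% test is 2 × [1 − Φ(1.96/√D)]. Both ICCs are assumptions.

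| ICC HRV / ICC event | D, m = 864 | Size, m = 864 | Size, m = 288 |
|---|---|---|---|
| 0.01 / 0.01 | 1.09 | 6% | 5% |
| 0.05 / 0.05 | 3.16 | 27% | 14% |
| 0.10 / 0.05 | 5.32 | 40% | 21% |
| 0.30 / 0.05 | 13.95 | 60% | 40% |
| 0.50 / 0.05 | 22.58 | 68% | 49% |
| 0.50 / 0.10 | 44.15 | 77% | 62% |

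Example: 1 + 863 × 0.50 × 0.05 = 22.6, √22.6 = 4.75, 1.96/4.75 = 0.41, size 68%. If either ICC is 0, D = 1 and the size is 5%.

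**4. Simulation with no true association, plain logistic regression on pooled epochs.**
- Beta-distributed event risk, events in 2% of epochs, N = 30, m = 864, HRV ICC 0.5, event ICC 0.05: 70% in one set of runs and 61% in an independent one.
- Normally distributed patient log-odds, about 1.8% event probability per epoch in a typical patient, HRV lag-1 autocorrelation 0.7, m = 864, N = 30 / 40: 17% / 19% (HRV ICC 0.3, log-odds SD 0.5), 52% / 48% (0.3, 1.0), 55% / 61% (0.5, 1.0), 75% / 74% (0.5, 1.5).
- Same model with m = 288, HRV ICC 0.3 and SD 0.5: 9% / 9%.
- With HRV ICC 0 or SD 0: 5% to 9%, which is nominal within simulation error at 300 runs per cell.

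**5. What repairs it.** Patient-clustered standard errors on the log-odds data brought the rate to about 4% to 16%, mostly 5% to 10%, so a small-sample correction is still needed at 30 to 40 clusters. Centring HRV on the patient's own mean gave about 3% to 7%, but only without serial correlation. With HRV and event risk both autocorrelated at 0.95, centring alone rejected in 21% of runs, against 8% with patient-clustered errors.

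**6. The other row units.** Day rows, using the 24-hour HRV, still give about three dependent rows per patient over 72 hours. Patient rows are independent but cannot show HRV before onset. All patients are mechanically ventilated (section 3.2), so most will plausibly have some ventilator change and that outcome would hardly vary.

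**The case against.** The strongest objection is that the protocol specifies no faulty analysis. It does not call the regression ordinary, make epochs the rows or declare them independent. Conditional and random-intercept models are logistic regressions too, and the row unit may be settled in an analysis plan not shown. Several outcomes in section 2.3 have one value per patient, and 24-hour HRV is available. All this is correct. A reader might infer that the plan treats epochs as independent; the text does not support that. The point survives because the synopsis and section 4.3 refer HRV analysis to the protocol's own statistical section, and the ordinary reading of the model named there suits no available row unit for recurring events.

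A reader might also infer that most reported HRV-event associations would be false. That does not follow. A false-positive rate is not the share of findings that are false, which also depends on power and on how many true associations exist; neither is known.

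Three further limits stand. The before-onset aim is stated for AF only; for the other events the protocol says only correlation, and the phrase "cardiorespiratory events that commonly occur in critically ill patients" describes a population, so recurrence within a patient is plausible but not stated. The simulations contain no covariates, whereas the plan adjusts for some and collects APACHE II and SOFA, which could absorb part of the between-patient variation. An event rate of 2% of 864 epochs, about 17 per patient, does not represent AF onset.

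**Conclusion.** The concern holds in a conditional form. For events that can recur during recording, the model named in the synopsis is a poor fit whichever row unit is chosen. If epochs are pooled in a plain logistic regression, the false-positive rate is well above 5% over most plausible ICCs, about 15% to 75%. It exceeds 50% only when HRV and event risk both vary strongly between patients, and it stays near 5% when either hardly varies. These sizes rest on assumed ICCs, event rates and autocorrelation. If rows are patients, the error rate is not the problem; the loss of timing is. The two outcome lists for the same model conflict on the face of the text, and ventilator-free days, length of stay and SOFA are not binary. This is a secondary analysis in a pilot, and the primary outcome of interpretable epochs is untouched, so the point should be corrected but does not threaten the study.

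**What to change.** In the synopsis, for events that recur within the recording, state the row unit and the pre-event window, and replace plain logistic regression with one of:

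- conditional logistic regression stratified by patient, comparing pre-event with event-free epochs of the same patient; or
- a patient random-intercept logistic model with separate terms for within-patient deviation and patient-mean HRV.

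In either case take standard errors by resampling patients or by patient clustering with a small-sample correction. Centring on the patient mean is not enough, because it leaves serial correlation untreated. Keep ordinary logistic regression for binary outcomes that occur once per patient, with one row per patient. Reconcile the outcome list in section 2.3 with that in the synopsis, and name a suitable model for the non-binary outcomes.

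The cost is wording and analysis code. Intervals become wider, and patients without an event do not contribute to the conditional model.
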